8.2.11.5. AE-Related Withdrawal of Consent

Any AE-related withdrawal of consent during the study must be reported by email or fax to USAMRDC ORA PSSO within 24 hours of event awareness. The WRAIR IRB will be notified of the withdrawal in a follow-up report as per [Table 8](#).

8.2.12. Pending Inspections/Issuance of Reports

The knowledge of any pending compliance inspection/visit by the FDA, Office for Human Research Protections (Department of Health and Human Services), or other government agency concerning clinical investigation or research, the issuance of Inspection Reports, FDA Form 483, warning letters, or actions taken by any regulatory agency including legal or medical actions and any instances of serious or continuing noncompliance with the regulations or requirements will be reported immediately to the WRAIR IRB and the sponsor's representative. The WRAIR HSPB will report knowledge of any pending inspections/audits by regulatory agencies to the USAMRDC OHARO OHRO as per USAMRDC Command Policy 21.

8.2.13. IND Annual Report to the FDA

The sponsor's representative will notify the PI of the due date of the annual report with sufficient time for the PI to assemble and submit all of the required clinical study information to the sponsor's representative.

The Sponsor and Sponsor's representative (USAMRDC) will be responsible for the preparation of the detailed annual synopsis of clinical activity, including AEs, for submission to the US FDA. Each annual report will summarize IND activity for one year beginning approximately 3 months before the IND US FDA anniversary date.

8.2.14. Final Report

A final study report will be prepared in accordance with "Guidance for Industry: Submission of Abbreviated Reports and Synopses in Support of Marketing Applications" and ICH E3 Guideline "Structure and Content of Clinical Study Reports" and provided to the sponsor's representative for review and approval. The sponsor's representative will use this report to prepare the final clinical study report for submission to the U.S. FDA.

Table 8: Sponsor's Adverse Event Reporting Requirements

Event	Report	Notification Time	Notification Method
Serious adverse events	SAE Report	Within 24 hours of event awareness ^a	Email: [name] [contact]
	Independent Safety Monitor Report	Within 24 hours of event awareness	
Pregnancy	Pregnancy Report	Within 24 hours of event awareness	If email is not available, the information can be faxed or called in: [contact] [contact]
Events of Special Interest (including PIMMCs)	SAE/AESI) Report	Within 24 hours of event awareness ^a	
	Independent Safety Monitor Report	Within 24 hours of event awareness	
Adverse Event Related Withdrawals	Contact PSSO	Within 24 hours of awareness of event awareness	
Safety-related Deviations	Contact PSSO	Within 5 business days of event awareness	

^a Submission of the reports to the PSSO must not be delayed. Do not wait to receive the independent safety monitor's report.

Table 9: Summary of Information Required When Reporting Adverse Events to the Sponsor

Information to Include on the Serious Adverse Event Report Form includes, but is not limited to:
Investigational new drug application number, sponsor study number Name of the investigational product Investigator name and contact number Subject identification number Serious adverse event term, description Onset date Date(s) of investigational product administration Severity Relationship to the investigational product Subject's current status Admission/Discharge Summary Consultations Medical record progress notes including pertinent laboratory/diagnostic test results

8.2.15. Pregnancy Reporting

Each pregnancy must be reported within 24 hours of identification by completing and submitting the Pregnancy Report Form by email or fax to the sponsor's safety office (ORA, Product Safety

Surveillance Branch (PSSO)). Pregnancies must be reported within 48 hours of becoming aware of the event to the IRB. WRAIR HSPB will forward the notification to USAMRDC OHARO OHRO as per USAMRDC Command Policy 21.

The following information will be reported on the Pregnancy Report: type and date of delivery, Apgar scores, and health status of the mother and child including the child's sex, head circumference, gestational age at delivery, length, and weight. Complications and or abnormalities should be reported including any premature terminations. A pregnancy is reported as an AE or SAE only when there is suspicion that the investigational product may have interfered with the effectiveness of contraception or there was a serious complication in the pregnancy including a spontaneous abortion or an elective termination for medical rationale. Otherwise, pregnancy will not be categorized as an AE.

8.2.16. Hepatitis B and C and HIV Reporting to the Local Health Authorities

Hepatitis B and C, and Human Immunodeficiency Virus (HIV) test results are required by law to be reported to the local health authorities. The test results reported to local health authorities will contain the participant's name, contact information, including address and telephone numbers, and the type of testing conducted.

8.2.17. Serious Adverse Event Follow-up

After the initial /SAE report, the investigator will proactively follow each subject at subsequent visits or contacts via phone or in person. All SAEs, and events of special interest, if applicable, will be followed until resolution, even if this extends beyond the prescribed reporting period. Resolution is the return to baseline status or stabilization of the condition with the probability that it will become chronic. The SAE outcomes will be reported to the ISM and ORA PSSO using the SAE Report Form. The investigator will submit any updated SAE data to the sponsor and ISM within 24 hours of receipt of the information.

If a subject dies during participation in the study or during a recognized follow-up period, the investigator will need to provide a copy of any post-mortem findings, including histopathology, if available.

Investigators are not obligated to actively seek SAEs in former subjects; however, if a SAE that is considered to be related to the investigational product occurs in a former subject and is brought to the attention of the investigator at any time following completion of the study, the event will be reported to the sponsor's representative ([Table 8](#)).

8.2.18. Safety Monitoring Committee

An independent safety monitoring committee (SMC) will be convened to review safety data and provide recommendations to the sponsor's representative. The SMC for this study will be comprised of an independent group of experts who will review cumulative safety data during scheduled in-process and ad hoc reviews to evaluate safety, study conduct, and scientific validity and integrity of the trial. The SMC will meet annually. After each review of study data, the SMC will make a recommendation to the sponsor's representative. The SMC recommendations will be documented and provided in writing (via the SMC Chair Recommendation Form) to the ORA PSSO. The sponsor's representative will then decide whether to continue, modify, or suspend the

study. The ORA PSSO will communicate the final decision to the investigator, who in turn will notify the IRB as appropriate. The ORA regulatory affairs scientist will communicate the final decision to the U.S. FDA, as appropriate. A further description of the SMC roles and responsibilities, functions, reporting requirements, meeting frequency, and the study stopping/continuation criteria is included in the SMC charter.

8.3. Immunogenicity Assessments

8.3.1. Specification of Immunogenicity Endpoints

Table 10: Immunology Assays

Humoral Assays	Serum or plasma	Function Measurement
ADCC, ADCP, and other non-neutralizing antibody functions	Frozen Plasma/ Serum	Measures lysis of HIV expressing targets mediated by HIV specific antibodies
HIV-specific binding	Frozen Plasma/ Serum	Binding antibody to vaccine antigens
HIV-specific neutralizing antibodies	Frozen Serum	Neutralizing activity against luciferase reporter gene expression
Cellular and Innate Assays	Serum or plasma	Function Measurement
Cellular response by cytokines such as IFN- γ and IL2 after stimulation with HIV-specific antigens	Frozen PBMC	CD4+ and CD8+ antigen-specific response
Lymphocyte proliferation	Frozen PBMC	Characterize the function of proliferating cells in response to HIV antigens
B-cell ELISPOT	Frozen PBMC	Measures cytokine secretion from B cells in response to HIV antigens
Flow cytometry for innate immune cell phenotyping and a cytokine array assay	Frozen Plasma/ Serum	Phenotype NK and other innate cells and characterize the cytokines elicited by the different vaccine regimens
DNA Microarray: gene expression to vaccine antigens	Frozen PBMC	Host gene expression profile and signature to vaccine antigens
RNA sequencing: gene transcription to vaccine antigens	Frozen PBMC	Host gene transcription profile and signature to vaccine antigens

8.3.2. Immunogenicity Endpoints

Immunogenicity will be assessed using the following assays at time points defined in the SOE.

8.3.3. Humoral Immune Responses

HIV-specific Binding Antibody ELISA Assays will be performed to detect serum or plasma IgG and IgA binding antibodies to HIV-1 gp120, in particular to the V1V2 loops. Capture antigens will include V1V2 sequences from both subtype AE and Subtype B HIV-1 Env (gp70V1V2 92TH023 and gp70V1V2 Case A2), and HIV-1 Env gp120 proteins matched to sequences in AIDSVAX® B/E without the gD tag and with an 11 amino acid N-terminal deletion, represented as gp120 A244gD- D11 and gp120 MNgD- D11. Durability of IgG response will be assessed for each participant by estimating the decline in log10 IgG from peak to 6 and 12 months post final vaccination.

Neutralizing Antibody Assays will be measured as a function of reductions in luciferase (Luc) reporter gene expression after a single round of infection in TZM-bl cells using high throughput analysis. Stocks of molecularly cloned envelope-pseudotyped viruses have been prepared by transfection in 293T/17 cells (American Type Culture Collection) and titrated in TZM-bl cells. This assay has been formally optimized and validated and was performed in compliance with Good Clinical Laboratory Practices (GCLP), including participation in a formal proficiency testing program. Tier 2 neutralization was assessed using a panel of 11 pseudoviruses, and a global panel.

Antibody Profiling will be conducted to assess antibody breadth and correlation of Fc receptor usage with antibody function. The current capacity for Antibody Profiling is the assessment of over 300 samples in one experiment. The beads presenting the HIV antigens will be distributed robotically in a high-throughput manner into 384 well plates. Similarly, the samples will be diluted robotically and incubated with the beads. Detection reagents will be added to the wells after washing. These detection reagents are inclusive of subclass, isotype and Fc receptor usage. Therefore, in one well, we will be able to capture 900 to 1000 data points from a single sample, and over 250,000 data points per experiment that will allow evaluation of the humoral immune response to these vaccine strategies.

Antibody-dependent cell-mediated cytotoxicity and antibody-dependent cellular phagocytosis will be evaluated using an amine reactive staining (Aqua) to identify killed target cells compare to loss of carboxyfluorescein succinimidyl ester (CFSE) in the traditional rapid and fluorometric ADCC (RFADCC). This Aqua-based assay is high throughput, has a better signal to noise ratio and a lower coefficient of variation than the conventional CFSE-based RFADCC assay. The ADCP phagocytic score will also be calculated and compared with Antibody profiling data to evaluate the impacts on IgG subclass and Fc receptor usage on non-neutralizing function between groups.

8.3.4. Cellular Immune Responses

Intra-cellular cytokine staining (ICS) assay. Cryopreserved peripheral blood mononuclear cell (PBMC) will be stimulated with HIV-specific antigens and gated on cell surface markers such as CD4 and CD8 to determine antigen-specific cellular responses by individual cytokines, such as interferon gamma (IFN γ) and interleukin 2 (IL2), as well as a composite, calculated functional and polyfunctional response using the COMPASS analysis method.

Cellular Proliferation. The proliferative responses of participant's PBMC to HIV-specific antigens and mitogens will be measured by the CFSE assay to characterize the function of proliferating cells.

B-cell Responses. A highly sensitive Env-specific B-cell ELISPOT system was developed, which allows the enumeration of antibody-secreting cells from diverse anatomical compartments directed against different structural determinants of HIV envelope. Both plasmablast and memory B cell responses will be quantified to detect gp120 A244-specific IgG producing plasmablasts and long-lived memory B cells using cryopreserved PBMC.

8.3.5. Innate Immunity

Characterization of Innate Immunity. Flow cytometric panels will be used to phenotype the different types of NK cells and functional ICS to characterize their function. Luminex® multiplex assays will be performed to compare soluble cytokines and other factors in plasma/serum across vaccine regimens, to further characterize innate biologic pathways engaged.

Innate and Early Adaptive Responses by Gene Activation Assessment. DNA microarrays will explore the innate and early adaptive immune responses to vaccination by screening genomic expression profile in PBMCs.

Transcriptomics. Transcriptome data will be generated using RNASeq to investigate gene expression that correlates with increased immunogenicity to particular vaccine combination.

8.4. Specimen Archiving and Transfer

Biological samples such as serum, plasma, PBMCs, whole blood, remaining after all assays described in this protocol have been completed will be bar coded and archived using electronic specimen storage and tracking system. PBMC will be stored at -125°C or lower and plasma/sera will be stored at -70°C or lower. Samples will be archived at the WRAIR Diagnostics and Countermeasures Branch (DCB) Specimen Processing Laboratory and Biorepository (SPL/BioR) indefinitely. If the study team determines to destroy these specimens, they will be destroyed per applicable SOPs of the archiving institutions. The PI, the Sponsor and authorized regulatory bodies may have access to the data regarding the archived specimens.

Archived samples will only be used for research and will not be sold; nor will study participants receive payment, should samples lead to the development of new products in the future. Any future study requesting these samples must first be reviewed and approved by the IRB of each applicable institute. With concurrence from these parties, archived specimens will be shipped to the U.S. Military HIV Research Program (MHRP) and collaborating laboratories for assays.

8.5. Future Use and Storage of Data and Biological Samples

Each participant will be asked to voluntarily consent to their data and blood samples to be stored for other research studies that may be done after this study is complete. Future testing may involve genetic tests. In case the participant is unwilling to have their data and/or biological samples stored for future use, they can consent to participate in this study only, without having their data and blood samples stored for future testing. In this case, their data and blood samples will be destroyed within one year of receiving notification from the PI that all protocol testing is

complete. Samples remaining in the biorepository will be destroyed by laboratory staff following approved laboratory procedures.

All data and samples for which consent has been obtained and for which additional material is available after study specified testing is complete will be stored indefinitely for future testing. However, WRAIR IRB approval will be sought before any such data and/or samples are used for analysis not specified in the protocol or a protocol amendment approved by the IRB. Data and samples may be shared with external collaborators but only after WRAIR IRB approval is received.

During the study, blood samples for safety testing will be tested as soon as possible and within the allowable sample stability timeframe for each test.

9. STATISTICS

This study intends to descriptively characterize safety and immune responses following administration of candidate vaccine A244/B.63521 with ALFQ adjuvant in healthy adults across three doses of ALFQ: 200 μ g, 100 μ g and 50 μ g, at baseline, month 1 and month 2. Statistical analysis will be performed on the following three groups:

- **Arm 1:** A244/B.63521 + 200 μ g ALFQ, N=20
- **Arm 2:** A244/B.63521 + 100 μ g ALFQ, N=20
- **Arm 3:** A244/B.63521 + 50 μ g ALFQ, N=20

Of specific interest is determining the safety of the candidate vaccine A244/B.63521 with ALFQ regimens as well as whether immunologic differences can be detected between the 3 study arms. Response rates, and, where applicable, titer level distributions with appropriate summary statistics will be estimated for each immunologic assay performed. The study will evaluate a series of cellular, humoral, and innate immune assays.

Due to limited sample size, rapid enrollment of subjects and short period of vaccination delivery over two months, no seasonal and other temporal effects are expected.

9.1. Statistical Criteria for the Termination of the Trial

There are no statistical criteria for the purpose of study termination in this clinical trial.

9.2. Procedures for Reporting Deviations from the Statistical Plan

Any deviation(s) from the statistical plan as indicated in the protocol will be described in an amendment to the protocol or the clinical study report. The protocol amendment will be submitted to the WRAIR IRB as per Section 10.1.1.

9.3. Accounting for Missing, Unused, and Spurious Data

Non-analyzable data will be documented in the deviations.

9.4. Sample size and Power calculation

The safety, reactogenicity, and tolerability of the vaccine regimens are the primary endpoints for this study. The table below demonstrates effect size with a power of 80%, calculated at a variety of sample sizes.

In [Table 11](#), the sample size calculation for the antibody titer (secondary outcome) will be based on the published data from Pitisuttithum P et.al¹⁸. For the analysis of this experiment we plan on observing a single measurement of peak antibody level per participant. Thus, the study is designed around a 1-way ANOVA model. Tukey's method will be used in the pairwise comparison test. In the analysis we looked at the size of the error bars on the peak of the log antibody titer and based upon our visual inspection we assumed that the residual standard deviation is = 0.2. A sample size of approximately 20 participants per arm was selected to provide $\geq 80\%$ power to detect the effect size of ≥ 0.202 between study arms. Statistical significance will be set at $p=0.05$.

[Table 12](#) depicts SAE or AESI rates and associated 95% confidence intervals in each potential grouping of interest given 0-5 participants with observed events. If we were to observe zero events within a single active study group ($n=20$), the upper limit of a 2-sided exact 95% CI would be 13.9% and true events above this could be ruled out at the $\alpha=0.025$ level.

Table 11: Sample size per arm and minimum effect size with 80% power, assuming residual standard deviation of 0.2

Part A: 3 Active Arms		
n per arm	Minimum effect size	Power
5	0.448	0.801
6	0.398	0.801
7	0.362	0.801
8	0.334	0.800
9	0.312	0.800
10	0.294	0.801
11	0.280	0.804
12	0.266	0.802
13	0.254	0.800
14	0.244	0.800
15	0.236	0.803
16	0.228	0.804
17	0.220	0.801
18	0.214	0.803
19	0.208	0.803

Part A: 3 Active Arms		
20	0.202	0.802
21	0.198	0.806
22	0.192	0.801
23	0.188	0.803
24	0.184	0.804
25	0.180	0.803
26	0.176	0.802
27	0.174	0.808

Table 12: Exact 95% Clopper-Pearson CI for the SAE Rate in Each Study Group

Number of Participants with Event	All Active Groups (n=60)	Any Active Group (n=20)	Arm 1 (n=22)	Arms 2 or 3 (n=19)
0	(0%, 4.9%)	(0%, 13.9%)	(0%, 12.7%)	(0%, 14.6%)
1	(<0.1%, 8.9%)	(0.1%, 24.9%)	(0.1%, 22.8%)	(0.1%, 26.0%)
2	(0.4%, 11.5%)	(1.2%, 31.7%)	(1.1%, 29.2%)	(1.3%, 33.1%)
3	(1.0%, 13.9%)	(3.2%, 37.9%)	(2.9%, 34.9%)	(3.3%, 39.6%)
4	(1.8%, 16.2%)	(5.7%, 43.7%)	(5.2%, 40.3%)	(6.0%, 45.5%)
5	(2.8%, 18.4%)	(8.7%, 49.1%)	(7.8%, 45.4%)	(9.1%, 51.2%)

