**Table S4: Exact 95% Clopper-Pearson CI for the SAE Rate in Each Study Group**

Number of Participants with Event	All Active Groups ( $n=60$ )	Any Active Group ( $n=20$ )
0	0% (0%, 4.9%)	0% (0%, 13.9%)
1	1.7% (<0.1%, 8.9%)	5.0% (0.1%, 24.9%)
2	3.3% (0.4%, 11.5%)	10.0% (1.2%, 31.7%)
3	5.0% (1.0%, 13.9%)	15.0% (3.2%, 37.9%)
4	6.7% (1.8%, 16.2%)	20.0% (5.7%, 43.7%)

Number of Participants with Event	All Active Groups (n=60)	Any Active Group (n=20)
5	8.3% (2.8%, 18.4%)	25.0% (8.7%, 49.1%)

Table S4 presents the estimated power for the secondary outcome of antibody titer based on the published data from Pitisuttithum P et.al. For the analysis of this experiment, we plan on observing a single measurement of peak antibody level per participant. Thus, the study is designed around a 1-way ANOVA model. Tukey's method will be used in the pairwise comparison test. In the analysis, we looked at the size of the error bars on the peak of the log antibody titer and based upon our visual inspection we assumed that the residual standard deviation is = 0.2. A sample size of approximately 20 participants per arm was selected to provide  $\geq 80\%$  power to detect the effect size of  $\geq 0.202$  between study arms. Statistical significance will be set at  $p \leq 0.05$ .

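### The zero-event row of the SAE/AESI interval table is a one-sided 95% bound: for 0 of 20 the two-sided limit is 16.8%, not 13.9%

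*Protocol*

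**What the plan says.** Protocol 9.4 introduces Table 12 as the precision available for SAE or AESI rates when 0 to 5 participants have an event. The worked example begins "If we were to observe zero events within a single active study group", with n=20. It states that "the upper limit of a 2-sided exact 95% CI would be 13.9% and true events above this could be ruled out", and adds that such rates "could be ruled out at the $\alpha=0.025$ level".

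SAP 4.4.1 carries the same sentence. The SAP table that goes with it (captioned Table S4, though the text calls it Table S3) is titled "Exact 95% Clopper-Pearson CI for the SAE Rate in Each Study Group", as is protocol Table 12.

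The zero-event row of protocol Table 12 gives upper limits of 4.9% (n=60), 13.9% (n=20), 12.7% (Arm 1, n=22) and 14.6% (Arms 2 or 3, n=19). SAP Table S4 keeps only the n=60 and n=20 columns, with the same 4.9% and 13.9%. Neither document calls the row one-sided.

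**The concern.** Method, sidedness, confidence level and alpha are all stated, so the upper limit for 0 of 20 has only one value, and 13.9% is not it. The row below it (1 of 20, 0.1% to 24.9%) is a genuine two-sided 95% interval, so the table changes definition between its first and second rows without a note.

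Safety is the primary endpoint, and this sentence is the one worked statement of safety precision in the sample-size section. Protocol 2.2.3 reports no SAEs in the three earlier ALFQ trials, so zero SAEs in an arm is a plausible result and this row may well be the one quoted. The error runs in the product's favour. SAP 5.1 and 7.1.2 call for exact 95% intervals at analysis. If they are computed two-sided, as Table S4 is labelled, an arm with 0 of 20 will be reported as 0% to 16.8%, which will not match the plan.

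**Working it through.** **Inputs.** Events x = 0; arm size n = 20; exact Clopper-Pearson; two-sided 95%; alpha 0.025 for the upper tail (all from Protocol 9.4). The other column sizes, 60, 22 and 19, come from Table 12.

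**Formula.** The two-sided 95% upper limit is the 0.975 quantile of a Beta(x+1, n−x) distribution. For x = 0 this reduces to 1 − 0.025^(1/n). The one-sided 95% upper bound for x = 0 is 1 − 0.05^(1/n).

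**Reproducing the printed row, then computing the interval the text names:**

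| n | Printed upper limit | 1 − 0.05^(1/n) (one-sided 95%) | 1 − 0.025^(1/n) (two-sided 95%) |
|---|---|---|---|
| 60 | 4.9% | 4.87% | 5.96% |
| 20 | 13.9% | 13.91% | 16.84% |
| 22 | 12.7% | 12.73% | 15.44% |
| 19 | 14.6% | 14.59% | 17.65% |

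The printed values equal the one-sided bound in all four columns.

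**Checking the alpha.** The probability of no events in 20 at a true rate p is (1 − p)^20.

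- p = 13.9%: 0.861^20 = 0.0501, so this rate is excluded at 0.05, not 0.025.
- p = 16.84%: 0.8316^20 = 0.0250, which matches the stated alpha.
- Read as an equal-tailed two-sided interval, 0% to 13.9% has confidence 1 − 2 × 0.0501 = 90%.

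**Checking the other rows.** For 1 of 20 the two-sided interval is 0.13% to 24.87%, as printed; the one-sided 95% upper bound would be 21.61%. Rows 1 to 5 agree with two-sided 95% limits in every column to within 0.1 point. Three n=19 limits differ in the last digit: 3 events, lower 3.38% (printed 3.3%); 4 events, 6.05% and 45.57% (printed 6.0% and 45.5%). These are trivial and separate from the fault in the zero row.

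**Other interval methods for 0 of 20.** Wilson gives 16.1%, Jeffreys 11.7% and the rule of three 15.0%. None gives 13.9%.

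**The case against.** **A software convention.** With no events the lower limit is fixed at zero, and some programs then put all of alpha in the upper tail, which yields 13.9%. This probably explains where the number came from. It does not rescue the sentence, because the exclusion level is then 0.05, while both documents call the interval two-sided and give 0.025.

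**Little depends on it.** The sample size rests on peak antibody titre. Protocol 9.1 sets no statistical criteria for termination, and the pausing rules in Protocol 8.2.11.3 are event counts. Reported intervals will be computed from the data. All of this is true: the fault is confined to a planning statement and does not pass into the results. It is still an incorrect figure about the primary endpoint.

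**The safety content is wider than this row.** Rows 1 to 5 are also quantitative safety statements and are sound. That zero is a plausible count is an inference from earlier SAE experience; the documents give no expected rate, and AESIs include a long list of immune-mediated conditions followed for 12 months.

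**The n=22 and n=19 columns may be deliberate.** Protocol 4.3 allocates six sentinels 4:1:1 and then enrols 54 more. Split equally, that gives 4 + 18 = 22, 1 + 18 = 19 and 1 + 18 = 19, a total of 60. This is very likely their source. The protocol does not say so, however. It plans 20 per arm in sections 1.2, 4.1 and 9, and SAP 4.4.2 aims for an overall 1:1:1 balance. The columns therefore need explaining or removing.

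**Conclusion.** The concern holds. For the interval described in Protocol 9.4 and SAP 4.4.1 (two-sided, exact, 95%, alpha 0.025), the upper limit for 0 of 20 is 16.8%. The printed 13.9% is the one-sided 95% bound, with an error probability of 0.050. No reading makes the figure, the two-sided 95% label and the 0.025 level true together.

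The overstatement of precision is 16.8 − 13.9 = 2.9 percentage points per arm of 20 and 6.0 − 4.9 = 1.1 points for all 60. The whole zero-event row is affected: four cells in the protocol and two in the SAP. The conclusion uses only the documents' own stated method and sample sizes, with no assumption about event rates. It leaves sample size, endpoints and planned analyses unchanged.

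**What to change.** Choose one consistent reading and apply it in Protocol 9.4 with Table 12 and in SAP 4.4.1 with Table S4.

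- **Preferred:** keep the two-sided 95% and alpha 0.025 wording. Change the zero-event upper limits to 6.0% (n=60) and 16.8% (n=20), and change 13.9% to 16.8% in the sentence. If the protocol keeps its other two columns, they become 15.4% (n=22) and 17.6% (n=19).
- **Alternative:** keep the printed row, footnote it as a one-sided 95% bound, and reword the sentence to say one-sided with alpha 0.05.

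In the protocol, drop the n=22 and n=19 columns, or add a note on their origin and reconcile them with the planned 20 per arm. State in the SAP that exact intervals for zero counts will be two-sided (or not), so that the final tables match the plan.

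The cost is one table row and one sentence per document, plus the short SAP statement and column note. Under the preferred option the quoted ceiling becomes slightly less favourable.
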